## 7.4.6.2 Storage

Describe the plans to store, handle the test article so they will be used only on subjects and only by authorized investigators. Describe storage temperature requirements and how temperature will be monitored and recorded.

n/a

#### 7.4.6.3 Preparation and Dispensing

Describe how the test article will be assigned to each subject and dispensed. Describe the steps necessary to prepare the test article. Include where the test article preparation will be done and by whom. Fully describe how the study treatment is to be administered and by whom.

n/a

#### 7.4.6.4 Return or Destruction of the Test Article

Describe the procedures for final reconciliation of the test article supply at the end of the study and whether the test article is to be shipped back to a source or destroyed on site.

n/a

## 7.4.6.5 Prior and Concomitant Therapy

Describe what prior and/or concomitant medical therapy will be collected. Describe which concomitant medicines/therapies are permitted during the study. Describe which concomitant medicines are not permitted during the study.

n/a

# 8.0 Subject Numbers and Statistical Plan

#### 8.1 Number of Subjects

Indicate the total number of subjects to be accrued.

If applicable, distinguish between the number of subjects who are expected to be enrolled and screened, and the number of subjects needed to complete the research procedures (i.e., numbers of subjects excluding screen failures.)

We expect to screen 1000 dyads (patients/caregivers) and enroll 458-468.

We plan to enroll ten nurse champions (2 per intervention unit, a high estimate with a plan for replacement if needed).

We plan to enroll approximately 6-8 nurses for focus groups from each intervention unit at the conclusion of the intervention, with a high estimate of a total of 35 nurses. This number is based upon our past experience recruiting for focus groups in this type setting, and the expected number to reach data saturation. However, if more than nurses volunteer/ want to participate, and/or the responses indicate the need to elicit more participation, we will add focus groups at the site.

We will oversample by 20-30 patients in order to continue promoting diversity.

#### 8.2 Sample size determination

If applicable, provide a justification of the sample size outlined in section 8.1 - to include reflections on, or calculations of, the power of the study.

We target a total sample size of 438 with 73 per inpatient unit is sufficient to detect an intervention effect comparable to the observed effect size in our pilot study, with 80% statistical power assuming a 20% attrition rate.

Our last site afforded us the opportunity to increase diversity; we will oversample by 20-30 patients in order to continue promoting diversity.

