## 7.4.3 Method for Assigning Subject to Treatment Groups

Describe the randomization process and how the associated treatment assignment will be made.

After the hospitals are randomized to the time cohort, within each six hospitals the two inpatient units will be randomly assigned so that one unit will receive Fam-FCC and the other unit will receive Staff-Ed (control) intervention. Random assignment will be completed by the statistician using SAS proc plan which specifically allows simultaneous randomization on multiple dimensions (time and units) as well as counterbalancing across units.

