#### 8.3 Statistical methods

Describe the statistical methods (or non-statistical methods of analysis) that will be employed.

Aim 1: Validate the efficacy of Fam-FFC on physical function (ADLs/ performance and physical activity), delirium occurrence and severity, behavior, and mood. For each outcome, an appropriate mixed effects model (either a LME or a GLMM) will be identified for model fitting. For delirium occurrence (a binary variable) we will use generalized linear mixed models with a logistic link function. The primary independent variables will be GROUP (Fam FCC v. control), TIME (day of admission, day of discharge, 2-month post discharge and 6-month post discharge) and SITE (for the three hospitals). The TIME x GROUP interaction will be tested for differential rate of change in the outcome. The GROUP x SITE interaction will be tested for heterogeneous center effects. Three-level models using an unstructured correlation will be fitted for the repeated measures within individuals who are nested within the same inpatient unit. 181-184 Time will be modeled continuously using day since admission so that trajectories can vary across individuals depending on time spent in the inpatient unit. This also allows us to examine non-linear time functions (e.g., quadratic) that allow the rate of change to vary over the different intervals. Covariates identified from the baseline analyses will be included in the mixed model to adjust for their influences. We will also consider interactive effects among demographic variables of interest (e.g., age, gender of patient and caregiver, ethnicity) and treatment condition to identify moderators of the treatment effects. Bootstrap methods will be applied to the mixed effects models in addition to the Wald test and the likelihood ratio test within the mixed effects models. 185-187 Subject level propensity score matching will be applied to improve the statistical power of the planned hypothesis tests.  To address the multiple endpoints issue in this trial, P<0.05 for the primary hypothesis and then multiple testing procedures such as closed testing implemented in PROC MULTTEST will be applied to adjust p values. 188-190

Aim 2: Evaluate the impact of Fam-FFC on family CG-centered outcomes (family CG preparedness for caregiving, strain, burden, and desire to institutionalize). LME similar to Aim 1, will be used.

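### Section 8.3 gives no small-sample reference for a treatment contrast resting on six randomised units, and the 80% power in section 8.2 cannot be verified for that contrast

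*Combined protocol and SAP*

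**What the plan says.** **Design.** Section 7.1 randomises units as clusters. Section 7.4.3 says that "the two inpatient units will be randomly assigned so that one unit will receive Fam-FCC and the other unit will receive Staff-Ed". Sections 4.2 and 16.1 give six units in three hospitals. Section 7.4.3 refers to six hospitals at one point, but 438/73 = 6 units agrees with the other sections.

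**Power.** The whole justification in section 8.2 is that 438 dyads, 73 per unit, are "sufficient to detect an intervention effect comparable to the observed effect size in our pilot study, with 80% statistical power assuming a 20% attrition rate". Section 2.1 calls the pilot effects moderate. For the patient outcomes, section 2.2 gives only chi-square and p-values. Its one standardised effect, a partial eta-squared of .06, is for caregiver preparedness.

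**Analysis.** Section 8.3 lists GROUP, TIME and SITE as the main model terms. Its statements that bear on this point are:
- On how clustering enters the model: "Three-level models using an unstructured correlation will be fitted for the repeated measures within individuals who are nested within the same inpatient unit".
- On which tests are used, where no reference distribution is given: "Bootstrap methods will be applied to the mixed effects models in addition to the Wald test and the likelihood ratio test".
- On the comparison of change between arms: "The TIME x GROUP interaction will be tested for differential rate of change in the outcome".
- On power, with no amount of gain stated: "Subject level propensity score matching will be applied to improve the statistical power of the planned hypothesis tests".
- On whether the effect differs by hospital: "The GROUP x SITE interaction will be tested for heterogeneous center effects".

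Section 8.3 also sets P<0.05 for a primary hypothesis that it does not identify. It gives no sidedness, no df method and no unit-level random slope, and it does not say what the bootstrap resamples.

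**The concern.** The three-level model recognises the clustering, but the reference distribution for the test is left open. Wald and likelihood-ratio tests normally use a large-sample cut-off. With three units per arm, the unit-to-unit variance is estimated on very few df, so that cut-off can be too lenient and a positive result can carry more than a 5% error rate.

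The same gap affects the reading of a null result. The 80% in section 8.2 is the only statement of what the trial can detect. If it does not apply to the contrast tested, a null result will look more informative than it is. Patient numbers do not remove the problem, because neither oversampling nor matching adds a randomised unit.

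**Working it through.** **1. The plan's own figure.** 6 × 73 = 438. After 20% attrition, 73 × 0.8 = 58.4 per unit and 3 × 58.4 = 175.2 per arm. The sums agree. The 80% cannot be reproduced, because effect, SD or rates, ICC, sidedness and df are absent. Solving backwards (two-sided 0.05, normal approximation, design effect 1 + 57.4 × ICC), 438 gives 80% for all of these pairs: 0.30 SD with ICC 0, 0.4 SD with 0.014, 0.5 SD with 0.031 and 0.6 SD with 0.053. Nothing in the documents selects one.

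**2. Unit-level df.** There are six unit means.
- Intercept and GROUP: 6 − 2 = 4 df.
- Adding SITE (three hospitals, 2 parameters): 6 − 4 = 2 df.
- Adding fixed GROUP × SITE (2 more parameters): 0 df, because the six units are the six GROUP × SITE cells.

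The two-sided 5% critical values are 4.30 (2 df) and 2.78 (4 df), against 1.96.

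**3. Type I error of a 1.96 Wald cut-off.** Simulated with balanced data, 58.4 patients per unit, 400,000 runs, and the unit variance constrained to zero or above as in a usual mixed model. The ICCs are assumptions.

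| ICC | 0 | 0.01 | 0.02 | 0.05 |
|---|---|---|---|---|
| SITE fitted | 4% | 7.5% | 10% | 14% |
| No SITE | 4% | 7% | 9% | 11% |

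The upper limits are 18.9% (2 df) and 12.2% (4 df). They are the error of a unit-mean t statistic referred to 1.96.

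**4. What a large-sample 80% becomes.** It implies effect/SE = 1.96 + 0.842 = 2.802. By the noncentral t, power at 2.802 is 35.2% on 2 df and 56.4% on 4 df. To reach 80% the ratio must be 5.653 (2 df) or 3.761 (4 df).

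**5. Illustration at 0.5 SD.** This is one assumed reading of moderate, with one outcome measure, no covariate gain and no between-hospital variance. SE = √[2(1 + 57.4 × ICC)/175.2], which is 0.107, 0.134, 0.157 and 0.210 at the four ICCs.

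| ICC | 0 | 0.01 | 0.02 | 0.05 |
|---|---|---|---|---|
| Power, 2 df | 67% | 52% | 42% | 28% |
| Power, 4 df | 93% | 79% | 67% | 44% |
| 80% detectable, 2 df (SD) | 0.60 | 0.76 | 0.89 | 1.19 |
| 80% detectable, 4 df (SD) | 0.40 | 0.50 | 0.59 | 0.79 |

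Enrolling 468 (section 8.1), spread evenly, raises the 2 df powers by at most about 2 points.

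**6. TIME × GROUP.** If units differ only in level, that difference cancels from the change and the contrast is judged against patient-level variation. A large-sample 80% then stays at about 79–80% (noncentral t with 100 to 340 df). If change varies between units, the df in step 2 apply.

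**The case against.** The strongest reply is that the plan is under-reported rather than wrong. The pilot effect may be large: on 4 df, 0.6 SD keeps 80% up to an ICC of about 0.02, and 0.8 SD up to about 0.05. Covariates may help: removing an assumed 36% of the variance lifts 2 df power at 0.5 SD and ICC 0 from 67% to 82%. The hypotheses are directional, and a one-sided 0.05 test at 0.5 SD and ICC 0.01 gives 76% (2 df) or 92% (4 df), against 52% and 79% two-sided. The only test that section 8.3 describes for change over time is TIME × GROUP, which may escape the df penalty. A bootstrap is also planned.

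Most of this stands, and it rules out two stronger readings. A reader might infer that true power is 35%. The documents do not support that: it needs a large-sample calculation with the correct variance, a unit-level GROUP contrast and a two-sided test with SITE fitted, and they do not show the calculation. A reader might also infer a type I error of 19% or 12%. Those are upper limits, and a mixed model that sets a small unit variance to zero inflates the error less.

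The reply does not settle which reference distribution is used. The bootstrap is unspecified, propensity matching has no stated gain, and without a stated random slope the plan does not show which case TIME × GROUP falls under.

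**Conclusion.** The point holds for section 8.3. For a treatment contrast that varies between units, the named large-sample tests have no adequate reference with six units. Two-sided type I error is about 4% to 14% with SITE and 4% to 11% without, over assumed ICCs of 0 to 0.05. There is no inflation at ICC 0. For TIME × GROUP this applies only if change over time varies between units.

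For section 8.2 the conclusion is narrower: the 80% cannot be verified. If it was a correct-variance large-sample figure for a unit-level GROUP contrast, two-sided power is about 35% (2 df) or 56% (4 df). It stays near 80% for TIME × GROUP if units differ only in level. All effect sizes and ICCs used here are assumptions, on a continuous scale with equal unit sizes.

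**What to change.** **Section 8.3, suggested text:** *The unit-level treatment contrast will be referred to a t distribution with fixed between-unit degrees of freedom (paired unit-mean analysis within hospital, 2 df), in a model without fixed GROUP × SITE. GROUP × SITE will be reported separately as a descriptive check. If TIME × GROUP is the primary contrast, the model will include a unit-level random slope. Large-sample Wald or likelihood-ratio references will not be relied on for this contrast. A null result will be interpreted by its confidence interval.*

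Two apparent alternatives do not solve the problem. A Satterthwaite-type df, in a simplified version that uses residual df when the unit variance is estimated at zero, still gives about 7% error with SITE at ICC 0.05. A permutation test over the within-hospital assignments has 2³ = 8 allocations, so its smallest two-sided p is 2/8 = 0.25.

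**Section 8.2, suggested text:** *Sample size was set for [endpoint] and [contrast, time point], using a pilot effect of [value and scale]. There are three units per arm, 73 enrolled and about 58 completers per unit. With a unit ICC of [range], a covariate gain of [ ]%, a [one- or two-]sided test and [ ] df, power is [ ]% (range [ ]) and the effect detectable with 80% power is [ ].* The team fills the brackets from its pilot data.

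**Cost.** Rewording only, with no added patients, units or visits. The stated power will probably fall. The fixed-df test also loses power if the true ICC is near zero: at 0.5 SD it has 67% on 2 df, against over 99% for a patient-level test. That is the price of holding 5% when units may differ.

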#### 8.3 Statistical methods

Describe the statistical methods (or non-statistical methods of analysis) that will be employed.

Aim 1: Validate the efficacy of Fam-FFC on physical function (ADLs/ performance and physical activity), delirium occurrence and severity, behavior, and mood. For each outcome, an appropriate mixed effects model (either a LME or a GLMM) will be identified for model fitting. For delirium occurrence (a binary variable) we will use generalized linear mixed models with a logistic link function. The primary independent variables will be GROUP (Fam FCC v. control), TIME (day of admission, day of discharge, 2-month post discharge and 6-month post discharge) and SITE (for the three hospitals). The TIME x GROUP interaction will be tested for differential rate of change in the outcome. The GROUP x SITE interaction will be tested for heterogeneous center effects. Three-level models using an unstructured correlation will be fitted for the repeated measures within individuals who are nested within the same inpatient unit. 181-184 Time will be modeled continuously using day since admission so that trajectories can vary across individuals depending on time spent in the inpatient unit. This also allows us to examine non-linear time functions (e.g., quadratic) that allow the rate of change to vary over the different intervals. Covariates identified from the baseline analyses will be included in the mixed model to adjust for their influences. We will also consider interactive effects among demographic variables of interest (e.g., age, gender of patient and caregiver, ethnicity) and treatment condition to identify moderators of the treatment effects. Bootstrap methods will be applied to the mixed effects models in addition to the Wald test and the likelihood ratio test within the mixed effects models. 185-187 Subject level propensity score matching will be applied to improve the statistical power of the planned hypothesis tests.  To address the multiple endpoints issue in this trial, P<0.05 for the primary hypothesis and then multiple testing procedures such as closed testing implemented in PROC MULTTEST will be applied to adjust p values. 188-190

Aim 2: Evaluate the impact of Fam-FFC on family CG-centered outcomes (family CG preparedness for caregiving, strain, burden, and desire to institutionalize). LME similar to Aim 1, will be used.

Aim 3: Evaluate the relative costs for Fam-FFC v. control condition, and calculate health care and total cost savings for Fam-FFC. Standard micro-costing methods will be used to estimate costs. Using the guidelines offered by Chatterji and colleagues, 191 total intervention costs will be based on expenditures/outlays for each of the following: (1) intervention; (2) consultant fees; (3) personnel costs, (4) incentives, meals, travel for study participants; (5) utilities, maintenance, security and other operating costs; and (6) administrative costs. We will identify all of the "inputs" that go into the implementation and then assign unit costs to these inputs (wages/salaries acquired from the unit managers, cost of materials, etc.). Then, we will multiply the units of inputs by their unit costs and sum this across all of inputs to determine the total cost of implementation per setting. An average across all settings will then be calculated. To estimate the cost of healthcare for each group, we will collect unit costs from existing literature including data published yearly by the American Medical Association, the American Hospital Association, the National Hospital Discharge Survey, and the American Managed Behavioral Healthcare Association. Similarly, these unit cost estimates for each type of health care utilization (emergency room, hospital and long-term nursing home admissions) will then be multiplied by the number of units used by each individual in the sample. A variable will be created for total health care cost by summing across conditions while exercising care to avoid any double counting of services. Health care and total cost savings will be calculated for each treatment condition. Mean costs and savings will be computed and subsequently tested for statistical significances across conditions using a t-test. In calculating cost we will also take into account fixed versus variable costs adjusting for variation over time in wages, benefits, and supplies using a standard micro-costing approach. We will then use multivariable regressions to determine whether Fam-FCC is significantly related to lower costs of healthcare and total cost savings controlling for covariates. Moreover, we will compare health care costs in terms of changes over time with paired t-test (within group differences) and with parametric Analysis of Variance (between group differences).

Assessment of the cultural appropriateness of Fam-FCC for diverse families in our sample: We employ the Ecological Model (EM) originally developed by Bernal and colleagues as a framework to assess the cultural appropriateness of the Fam-CC intervention and to refine Fam-FCC for future studies. See below for analysis plan.

EM Model Component	Sample/Data Source	Analysis
I. Family-CG experiences of EM model constructs (categories 1,3,4,5,6,8)	Caregivers who self-identify as black, Latino, Asian and white will be randomly selected (Approximately 10% of families from each ethnic group; if theoretical saturation is not reached, interviews will continue until saturation is reached.) A draft semi-structured interview guide will be refined with the input of a hospital patient /family council.	Qualitative content analysis of audiotaped, transcribed interviews conducted at the six-month post-hospital discharge contact. Trustworthiness  is enhanced by the team's methodological expertise, random sampling, rigorous analytic approaches, member checking, and a detailed audit trail.
II. Nurse champion experiences of EM model constructs (categories 1,3,4,5,6,8)	The six champions (2 per setting) will be interviewed using a semi-structured interview guide.	Qualitative content analysis of audiotaped, transcribed interviews at conclusion of intervention at each site.
III. Evaluation of measures for reliability and validity for the ethnic groups represented in the study (category 7)	1)The internal consistency of the caregiver outcome measures as well as relationships with known correlates (e.g., educational level) will be evaluated in the first 20 Spanish-speaking respondents and 2) Both content and face validity of each measure will be discussed in participant interviews outlined in Component I above.	Cronbach's alphas for caregiver outcomes will be assessed.  The participants will be asked to assess their perceptions of measures and identify potential cultural gaps in measurement content in Component I above.
IV. Assessment of whether ethnic concordance moderates the relationship between treatment group and patient/ family outcomes (category 2).	The ethnicities of nurse champions and each family will be documented as concordant or not.	Concordance will potentially be used as a covariate in analyses for specific aims 1, 2.

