Depression	Cornell Scale for Depression in Dementia (CSDD) 	A 19-item survey designed to assess depressive symptoms in individuals with dementia. 154, 155 There is sufficient evidence of reliability and validity. 155	
NPS	Brief Neuropsychiatric Inventory (NPI-Q) 	A 12-item, reliable, validated informant-based assessment of neuropsychiatric symptoms and associated caregiver distress. 156	

Adverse Events	Report of falls, hospitalizations,	A monthly check of the patient hospital record to evaluate for
	transfers to the emergency	hospitalizations/ED visits (in addition to the family caregiver
	department	report at month 2 and month 6).

The following outcome measure data collection will be initiated within 72 hours of discharge (T1), and 2 month (T2) and 6 month post-discharge (T3), by research evaluators via interview of the patient/family CG

Family Caregiver Outcome Measures- collected for both control and intervention group.			
Aim 2: Evaluate the imp	Aim 2: Evaluate the impact of Fam-FFC on Family CG-centered outcomes.		
	All measures are self-rated and will be initiated within: 72 hours of discharge (T1), 2 (T2) and 6 months post-discharge (T3). This data is collected via pen/paper tools completed by family CG.		
Measure	Measure Tool Description		
Preparedness for caregiving	Preparedness for Caregiving Scale 	An 8-item instrument that asks caregivers how well prepared they believe they are for multiple domains of caregiving: physical care and emotional support, setting up support services, dealing with the stress of caregiving. Items are rated 0 (not at all prepared) to 4 (very well prepared); shows very good reliability and internal consistency, 157 including in family CGs of hospitalized persons with dementia. 59	
Caregiver Strain	Modified Caregiver Strain Index (CSI) 	A 13-question tool that measures strain (financial, physical, social, psychological, and personal) related to care provision, with excellent internal consistency and reliability. 158,159	
Caregiver Burden	Zarit Burden Interview (ZBI-12)  short version	12-item tool that measures caregiver perception of burden has shown high internal consistency and discriminative ability in caregivers of persons with dementia. 160,161	
Desire to Institutionalize	Desire to Institutionalize Scale 	6-item scale with moderate reliability; Cronbach alpha = 0.694.162	

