#### 7.4.2 Treatment Regimen

Describe dose, route of administration and treatment duration. Include information about dose adjustments.

The intervention begins during hospitalization. Post -acute follow-up will provide ongoing education and modification of the function-focused care plan (contact within 72 hours of discharge, weekly telephone calls for a total of 7 additional weeks, then monthly for 4 months).

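### Each GROUP x SITE cell is a single randomised unit, so the planned interaction test cannot show centre heterogeneity; any GROUP comparison on six units also needs a specified small-sample reference.

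*Combined protocol and SAP*

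**What the plan says.** All references are to the combined protocol and SAP.

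- **Design.** Section 7.1 randomises study units as clusters. Section 4.2 gives six units in three hospitals, and the site procedures in section 7.2 give two study units per site. Section 7.4.3 puts one unit of each hospital in each arm: "within each six hospitals the two inpatient units will be randomly assigned so that one unit will receive Fam-FCC". The count of six hospitals there conflicts with three elsewhere, but either reading leaves one unit per arm per hospital.
- **Model.** Section 8.3 lists GROUP, TIME and SITE as the primary independent variables. It adds: "Three-level models using an unstructured correlation will be fitted for the repeated measures within individuals who are nested within the same inpatient unit".
- **Tests.** Two tests involving treatment are stated for Aim 1: "The TIME x GROUP interaction will be tested for differential rate of change in the outcome" and "The GROUP x SITE interaction will be tested for heterogeneous center effects". On inference it says: "Bootstrap methods will be applied to the mixed effects models in addition to the Wald test and the likelihood ratio test". It gives no denominator degrees of freedom and does not say what the bootstrap resamples.
- **Aim 2.** The analysis is described only as "LME similar to Aim 1, will be used". In the section 7.2 outcome table, caregiver outcomes start at T1, after discharge. Section 7.4.2 says: "The intervention begins during hospitalization".
- **Size.** Section 8.2 targets 438 patients, 73 per unit, with 20% attrition. It states no ICC and no numerical effect size.

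**The concern.** A test for heterogeneous centre effects asks whether the treatment difference varies between hospitals by more than chance. Chance must include the ordinary variation between wards, because wards were randomised. With one ward per arm in each hospital, nothing is left from which to measure that variation. A significant result could then be reported as hospitals responding differently to Fam-FFC when two wards merely differ in staffing or case mix.

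The same shortage of units affects any comparison of the arms that is not a comparison of change. With three units per arm, a large-sample reference for GROUP gives p-values that are too small if wards vary. This matters most for Aim 2. Caregiver outcomes have no measurement before the intervention, so the part of a difference that is already present at T1 and stays constant appears in GROUP, where ward differences do not cancel.

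**Working it through.** **1. The plan's own figures.** 6 x 73 = 438. After 20% attrition, 438 x 0.8 = 350.4, or about 58 per unit. The 80% power in section 8.2 cannot be reproduced, because no effect size or ICC is given.

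**2. Unit-level degrees of freedom.** There are six unit means.
- Intercept, two SITE terms and GROUP: rank 4, leaving 6 - 4 = 2 df.
- Adding the two GROUP x SITE terms: rank 6, leaving 6 - 6 = 0 df.

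This needs no assumption. On the six-hospital reading there are 12 units and 12 cells, again leaving 0 df.

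**3. Why the three-level model does not help.** With the interaction fitted, each unit mean is matched exactly and the between-unit residual sum of squares is zero. The REML likelihood is then flat in the unit variance, and ML puts it at zero. The ML test therefore falls back on patient-level error. Extra patients or repeat visits add no units. The two-way term also averages over admission, so it carries ward differences that precede the intervention.

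**4. Size of the interaction test.** Assumptions: one continuous value per patient, 58 per unit, no covariates, no true heterogeneity, and ICC from 0 to 0.05. The variance of a unit mean relative to what patient-level error implies is

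R = 1 + 58 x ICC / (1 - ICC).

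The false-positive rate is P(F(2,342) > Fcrit / R), with 342 = 6 x 57. A hand check is 0.05^(1/R).

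| ICC | R | 0.05^(1/R) | F(2,342) |
|---|---|---|---|
| 0 | 1.00 | 5% | 5% |
| 0.01 | 1 + 0.58/0.99 = 1.59 | 15% | 15% |
| 0.02 | 1 + 1.16/0.98 = 2.18 | 25% | 25% |
| 0.05 | 1 + 2.90/0.95 = 4.05 | 48% | 48% |

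The ML likelihood-ratio test with a random unit term gives 5 / 16 / 26 / 48% by simulation. A three-level simulation with four occasions (unit share 0 / 1 / 2 / 5% of single-measure variance, 1,500 trials each) gave 5 / 21 / 34 / 58%. The estimated unit variance was zero in every fit that included the interaction.

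**5. GROUP main effect, with SITE in the model.** Null rejection rates from simulation under the assumptions of step 4:

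| Method | ICC 0 | 0.01 | 0.02 | 0.05 |
|---|---|---|---|---|
| Wald z, random unit (REML) | 4% | 8% | 10% | 14% |
| Likelihood ratio (ML) | 5% | 10% | 15% | 22% |
| GROUP x SITE kept in, patient-level error | 5% | 12% | 18% | 33% |
| Bootstrap resampling patients within units | 5% | 12% | 19% | 33% |
| Parametric bootstrap LR, ML null variance | 4% | 8% | 10% | 13% |
| Parametric bootstrap LR, REML null variance | 0.3% | 1.2% | 2.2% | 4.3% |
| t on three within-hospital differences, 2 df | 5% | 5% | 5% | 5% |

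The REML unit variance is estimated as zero in 47 / 37 / 22% of null trials at ICC 0.01 / 0.02 / 0.05, so default software df are unsafe.

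**6. TIME x GROUP.** If a unit adds the same amount at every visit, that amount cancels from change. Inflation would need units to differ in change over time. The documents give nothing on this, and the plan names no unit-by-time term.

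**The case against.** The strongest reply has four parts.

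- **A bootstrap is named.** This stands. Section 8.3 does name one, and the reference list includes titles on bootstrapping clustered data and on trials with few clusters. A reader might infer that the plan ignores small samples altogether; it does not. What is missing is the bootstrap's type, resampling level and role. That matters, because one form stays at or below 5% for ICCs up to 0.05 and others do not.
- **The stated efficacy test is TIME x GROUP.** This stands too. A reader might infer that the main Aim 1 test is inflated. The documents do not support that: a stable unit effect cancels, and a GROUP main-effect test is only implied.
- **Aim 2 is not tied to GROUP.** Partly right. A caregiver difference that grows or fades after T1 also enters TIME x GROUP, so it would be wrong to say that benefit can appear only in GROUP. Only the constant part is confined there.
- **The simulated model is not the planned one.** Correct. Section 8.3 plans covariates, continuous time, propensity matching and a logistic model for delirium. The figures are not the trial's error rates.

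None of this touches the interaction test, whose defect follows from the count of units. It is attached to none of H1 to H5, however, so misreading it would not by itself change an efficacy conclusion.

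**Conclusion.** The GROUP x SITE test cannot do what section 8.3 asks of it. That follows from the design, whatever the ICC. The size of the error does depend on the ICC: about 15 to 48% false positives for ICC 0.01 to 0.05 in the simplified model, and none beyond 5% at ICC 0.

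The secondary point is conditional. If GROUP is tested as a main effect on six units with a large-sample reference and the ICC is above 0, Wald z and likelihood-ratio tests reject too often: about 8 to 14% and 10 to 22% over the same range. The Wald figures assume a z reference, which the plan neither states nor rules out.

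A reader might also infer that the stated 80% power is wrong. The documents show only that it cannot be checked, which is a separate matter. This should be fixed before analysis, but it does not invalidate the trial.

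**What to change.** 1. Drop the GROUP x SITE hypothesis test and leave the term out of the confirmatory model. Report the three within-hospital differences descriptively, with no claim of centre heterogeneity.
2. For any GROUP main-effect comparison, including Aim 2, name one small-sample method whose size has been checked by simulation for six units. Two candidates are a t on the three within-hospital differences (2 df) and a parametric bootstrap likelihood-ratio test with REML null variance. State what the bootstrap resamples. The second has more power, but its size reaches 5.9% at ICC 0.10 and 6.5% at ICC 0.20.
3. Optionally, add a unit-by-time term or an analysis of unit-level change as a sensitivity analysis for TIME x GROUP.

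The cost is SAP wording and analysis time; no new data are needed. Intervals widen and power for GROUP falls. With SE = sqrt(2/3 x (ICC + (1 - ICC)/58)) and an assumed standardised difference of 0.50 (section 2.1 says only that pilot effects were moderate), the SE is 0.107 / 0.134 / 0.157 / 0.210 at ICC 0 / 0.01 / 0.02 / 0.05. Power is then 67 / 52 / 42 / 28% for the 2-df t, and 81 / 66 / 55 / 37% by simulation for the REML-null bootstrap. Covariate adjustment could recover part of this.
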